3.0 OBJECTIVES

The overall goal of the study is to assess whether 2 doses of vaccine are non-inferior to 3 doses. Participants will be randomized 1:1 to receive 3 doses of 9vHPV vaccine at the routine vaccine schedule of 0/2/6 months or at an extended schedule of 0/6/12 months.

1. **Primary Objective**
 - 1) Determine whether peak anti-HPV16/18 geometric mean titers (GMTs) to 2 doses of 9vHPV vaccine are non-inferior to peak anti-HPV16/18 GMTs to 3 doses at month 7.
2. **Secondary Objectives**
 - 2) Compare the antibody persistence at month 24 between the routine and extended vaccine schedule.
 - 3) Elucidate the acceptability of HPV self-sampling among WLWH in Canada.

3. Exploratory Objectives

- 4) Determine whether peak anti-HPV6/11/31/33/45/52/58 GMTs from 2 doses of 9vHPV vaccine are non-inferior to those from 3 doses at month 7.
- 5) Assess peak anti-HPV16/18 GMTs to 1 dose at month 1.
- 6) Describe the incidence, type, and severity of adverse events in WLWH.
- 7) Elucidate the efficacy of 9vHPV vaccination up to month 24 (via persistent HPV infection with 9vHPV types, and cytological and histological HSIL).
- 8) Engage in a BC Cancer Registry linkage to investigate rates of pre-cancer or cancer diagnoses.
- 9) Investigate the role of viral and bacterial co-infection in the development of cervical dysplasia and vaccine breakthrough HPV infection in WLWH
- 10) Assess the uptake of HPV vaccination in WLWH aged 18-45 across Canada prior to study.

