5.0 STUDY COHORT

1. Population

Recruitment of 450 WLWH aged 18-45 years is being performed by research staff at 10 sites across Canada. The 450 WLWH will be randomized 1:1 to two groups:

- 1) Three doses of 9vHPV vaccine at the routine dosing schedule of 0/2/6 months.
- 2) Three doses of 9vHPV vaccine at an extended dosing schedule of 0/6/12 months.

Inclusion Criteria

- Has a confirmed diagnosis of HIV infection
- Has a cervix (not have had their uterus removed)
- Age 18-45 years
- Not pregnant, and not trying to become pregnant
- Able to communicate in English if adequate translation is not available

Exclusion Criteria

- Unable to give fully informed consent
- Allergy to the vaccine or its components
- Prior receipt of any HPV vaccine.

Females aged <18 are excluded because all children, including those with HIV, are vaccinated in adolescent programs in Canada leaving very few eligible under that age. Further, we seek to inform the use of 9vHPV vaccine beyond adolescent program ages. The upper age limit of 45 years was chosen based on vaccine licensure as the 9vHPV vaccine is currently authorized for use in females ages 9-45.

Women will not be excluded based on baseline HPV immune status. All women can benefit from vaccination as they are virtually all seronegative for at least one 9vHPV type. Also, HPV seronegativity is not required for vaccination programs, thereby making our findings most relevant to vaccination programs, which would be conducted without a seronegativity requirement. We will assess baseline HPV immune status for use in post hoc outcomes analysis.

2. Randomization

Randomization will be stratified by site using permuted blocks of random size. A CIHR Canadian HIV Trials Network (CTN) statistician will computer-generate random allocations, which will be uploaded to a password-protected webpage. When an eligible consenting participant is identified, the webpage will issue a study identification number and vaccine regimen allocation. An automated audit trail will track date and time of transactions along with study identification number, stratum, and allocation. No placebo will be used as the primary aim of this study is to assess non-inferiority to different 9vHPV vaccine dosing regimens, not to compare outcomes to unvaccinated women.

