To determine if 2 doses of 9vHPV vaccine are non-inferior to 3 doses in WLWH, we will evaluate serologic response by comparing peak anti-HPV16/18 GMTs individually with 95% CI at 7 months in both groups using linear regression, adjusted for HIV viral load, CD4+ T cell count, and age.⁴⁶ We will similarly compare seroconversion rates in the two groups using logistic regression. Adjusting for age and HIV clinical parameters instead of stratifying by them (they are also unlikely to be importantly imbalanced in a trial this size) can improve sensitivity/power.⁴⁶ Using immunobridging,^{47,48} we will also compare the rate of seroconversion and peak anti-HPV GMTs to previously published two-dose 4vHPV responses in girls and women without HIV²³ and previously published three-dose 9vHPV responses in girls and women without HIV using logistic regression for seroconversion rates and one-sample t-tests for GMT comparisons.^{18,49} Immunobridging is a highly accepted method of evaluating HPV vaccines in different groups when a correlate of protection is unknown and efficacy endpoints such as cervical dysplasia take many years to develop. Level of antibody response after two doses will be described by clinical and demographic variables (age, CD4 count, HIV viral load, HPV DNA or antibody positivity at baseline, and lifetime number of sexual partners) using general linear models.

4. Secondary Analyses

1. To compare differences in antibody persistence, longitudinal GMTs will be compared between the two groups (routine vs. extended dosing interval) to determine if there are differences in the rates of antibody persistence at month 24. We will use mixed-effects linear regression on the log-transformed titers to estimate the rate of decline of antibody titers by time since first vaccine dose. Differences in rates will be compared directly using an interaction term between group and time.

2. To evaluate HPV self-sampling acceptability, quantitative survey results will be summarized as frequencies. Comparisons among subgroups (e.g. by age, region, cultural background, and gender) will be conducted using linear regressions.

5. Exploratory Analyses

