1. To determine if 2 doses of 9vHPV vaccine are non-inferior to 3 doses in WLWH for the additional 9vHPV types not in the primary outcome, we will evaluate serologic response by comparing peak anti- HPV6/11/31/33/45/52/58 GMTs individually and seroconversion rates with 95% CI at 7 months in both groups using linear and logistic regression, respectively, adjusted for HIV viral load, CD4+ T cell count, and age.
2. As the world is moving towards one-dose HPV vaccine schedules, we will take the opportunity to collect preliminary data on the peak one-dose antibody response at month 1. These data will inform the sample size calculation for a future one-dose trial, as appropriate, and will be reported as anti-HPV16/18 GMTs with 95% CI.
3. To evaluate significant adverse events, the proportion (and 95%CI) of participants who experience significant adverse events will be calculated for the entire study population, and also by group. The types and severities of adverse events will be described.
4. To address vaccine efficacy, we will calculate incidence rates of abnormal cervical cytology and histology (HSIL), and breakthrough persistent HPV infection. HSIL will be described with Kaplan-Meier curves. If sufficient numbers of each are observed, Kaplan-Meier curves will be calculated by age range (21-30, 31-39, 40-55, >55), CD4 count (<200, 200-500, >500), HIV viral load (detectable vs. undetectable), and prior HPV status. Persistent HPV will be described by type of HPV, high vs. low-risk, and vaccine type or not, using Kaplan-Meier curves for HPV acquisition and frequencies and percentage for persistent infections. Given the capability to intervene with early pre-cancerous changes in the cervix, we cannot ethically use cervical cancer as an end point but other efficacy endpoints are critical for an HPV vaccine study as an immune correlate of protection is unknown.
5. To assess the uptake of HPV vaccination of WLWH, a screening log will be kept by each study site to track how many WLWH aged 18-45 were not eligible to participate in the study due to having already received an HPV vaccine. The proportion of women who were previously vaccinated will be calculated for the population of women aged 18-45 at each site and across the country.

6. **Planned Subgroup Analyses**

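### Incidence rates of HSIL and persistent HPV infection in two vaccinated arms are labelled vaccine efficacy, with no reference rate and no stated rule for infection or lesions present at entry

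*Protocol*

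**What the plan says.** Objective 7 in section 3.0 (item 6 in the Summary) is to "Elucidate the efficacy of 9vHPV vaccination up to month 24", measured by persistent infection with vaccine types and by cytological and histological HSIL. Section 7.4.2 lists efficacy among the data the trial will supply. Section 13.5 item 4 gives the analysis: "To address vaccine efficacy, we will calculate incidence rates of abnormal cervical cytology and histology (HSIL"), and likewise for breakthrough persistent infection. HSIL is to be shown with Kaplan-Meier curves. Those curves are split by prior HPV status, among other factors, only if numbers suffice. For HPV infection the item plans curves for acquisition, and counts and percentages for persistence.

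On the comparison, section 3.0 says "Participants will be randomized 1:1 to receive 3 doses of 9vHPV vaccine at the routine vaccine schedule of 0/2/6 months", with the other arm receiving three doses at 0/6/12 months. Section 5.2 explains the absence of a placebo by saying the aim is "not to compare outcomes to unvaccinated women".

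On entry, section 5.1 says "Women will not be excluded based on baseline HPV immune status". The listed criteria do not exclude current HPV infection, abnormal cytology or HSIL either. On timing, section 13.3 says that "efficacy endpoints such as cervical dysplasia take many years to develop", while section 7.4.1 sets follow-up at 24 months.

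**The concern.** Efficacy compares what happened in vaccinated women with what would have happened without vaccine. An incidence rate in vaccinated women alone is not that comparison. A low rate could be read as protection and a high rate as vaccine failure, and the design could support neither reading.

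HSIL has a second problem. If dysplasia takes years to develop, a lesion found within 24 months may come from an infection that preceded the first dose. Counting it as an efficacy event charges the vaccine with disease it had no chance to prevent. The matter is more than a loose word, because item 4 itself calls efficacy endpoints critical on the ground that no immune correlate of protection is known. Readers are therefore likely to take these rates as the trial's efficacy evidence in women living with HIV.

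**Working it through.** The protocol states no event rate, power or target for this item, so there is no figure to reproduce. The sample size in section 13.7 concerns the month-7 titre comparison and has no bearing here.

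**1. Is there a comparator?** Both arms are vaccinated (sections 3.0 and 5.1). Section 13.5 item 4 names no external or historical rate. The published comparisons in section 13.3 cover GMTs and seroconversion only. At most, the data can describe incidence after vaccination or compare the two schedules.

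**2. What does a rate alone say about efficacy?** Efficacy = 1 - (rate in vaccinated / rate in unvaccinated). Assume 2 per 100 person-years in the vaccinated and vary the missing rate:
- unvaccinated 1: 1 - 2/1 = -100%
- unvaccinated 2: 1 - 2/2 = 0%
- unvaccinated 4: 1 - 2/4 = 50%
- unvaccinated 8: 1 - 2/8 = 75%

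The same observed rate fits all four values.

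**3. Is HSIL present at entry, or arising from infection at entry, separated?**
- Eligibility (section 5.1) does not remove it.
- Tables 1A and 1B and the visit outline in section 7.4.5 contain no cytology. HSIL is therefore known only when care outside the study procedures finds it, and no step attributes it to an HPV type.
- The split by prior HPV status in section 13.5 depends on numbers.
- The subgroups by baseline HPV DNA or antibody in section 13.6 cover primary and secondary analyses, not this exploratory item.
- Section 5.1 assigns baseline immune status to post hoc analysis.

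**4. How large could the share from women infected at entry be?** Let p be the share infected at entry, RR the HSIL risk ratio of infected to uninfected women without vaccine effect, and VE the efficacy against new infection, with none assumed against existing infection. Then:

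share = p·RR / [p·RR + (1 - p)(1 - VE)]

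The documents give none of these inputs. The background section gives only a relative figure, twice the prevalence seen in women without HIV. All values below are assumptions.

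| p | RR | VE = 0 | VE = 90% |
|---|---|---|---|
| 0.1 | 2 | 0.2/(0.2 + 0.9) = 0.18 | 0.2/(0.2 + 0.09) = 0.69 |
| 0.1 | 5 | 0.5/(0.5 + 0.9) = 0.36 | 0.5/(0.5 + 0.09) = 0.85 |
| 0.2 | 5 | 1/(1 + 0.8) = 0.56 | 1/(1 + 0.08) = 0.93 |
| 0.3 | 10 | 3/(3 + 0.7) = 0.81 | 3/(3 + 0.07) = 0.98 |
| 0.5 | 20 | 10/(10 + 0.5) = 0.95 | 10/(10 + 0.05) = above 0.99 |

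The better the vaccine works against new infection, the more the remaining HSIL comes from infection it could not prevent.

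**5. Would an external reference rate alone repair the HSIL result?** No. With VE = 90% against new infection, efficacy over all women is 1 - [p·RR + 0.1(1 - p)] / [p·RR + (1 - p)]. For p = 0.1 and RR = 5 this is 1 - 0.59/1.40 = 0.58. For p = 0.5 and RR = 20 it is 1 - 10.05/10.50 = 0.04. The at-risk set matters as well as the comparator.

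**6. Persistent infection.** Section 13.5 uses the words *breakthrough* and *acquisition*, which point to new infection. Neither is defined, and no rule says what happens to a type already present at month 0.

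**The case against.** The case for leaving the text alone has real strengths. The item is exploratory and descriptive: it plans rates, curves and frequencies, and no efficacy percentage, test or threshold. The lack of an unvaccinated group is stated openly in section 5.2. Enrolling regardless of baseline status is reasoned, because vaccination programmes do not require seronegativity. The sentence on slow development of dysplasia explains why immunobridging is the primary approach, which fits with efficacy being only exploratory. Abnormal Pap tests, colposcopies and treatments are recorded at month 0 and updated (section 7.5.2), and a month-0 DNA swab is taken. Finally, at-risk definitions are often left to an SAP, which is not at hand.

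Most of this stands and limits the weight of the point. It does not rescue the label. An SAP can define who is at risk, but it would do so beneath a protocol objective that already calls uncontrolled rates efficacy.

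A reader might go further in two ways that the documents do not support:
- One might infer that any type found at months 0 and 6 will be counted as a persistent infection, from the passage in section 12.2 on the same high-risk type found twice at least six months apart. That passage says when primary care providers are notified. It is not adopted as an endpoint definition, so no count of wrongly included infections can be built on it.
- One might conclude that the results will mainly reflect disease present before vaccination. That is plausible for HSIL, but without a baseline prevalence or HSIL rate it cannot be shown. The lowest cell of the table is 0.18.

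**Conclusion.** The point holds in two parts. First, the planned rates cannot estimate vaccine efficacy. This follows from the design as written and needs no assumption about prevalence; the -100% to 75% range only illustrates it. Second, the main HSIL rate has no stated rule separating women infected or with lesions at entry, so an unknown and possibly large share of events may stem from infection before dose 1. The illustrated shares, 0.18 to 0.95 without vaccine effect and 0.69 to above 0.99 with 90% efficacy against new infection, rest wholly on assumed inputs. They show sensitivity and are not estimates for this cohort. For persistent infection the gap is narrower: the wording suggests new infection, and what is lacking is a stated rule that excludes types present at month 0. The month-7 immunogenicity conclusion is not affected.

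**What to change.** - In objective 7, the matching Summary item and section 13.5 item 4, replace the efficacy wording with incidence of HSIL and breakthrough persistent infection after vaccination, and bring section 7.4.2 into line. State that no vaccine efficacy estimate will be claimed.
- Make the main persistent-infection rate type-specific, among women DNA-negative for that type at month 0.
- Report HSIL overall. Also report it, as the main rate and not only if numbers suffice, among women who are DNA-negative for 9vHPV types at month 0 and have no current or unresolved abnormal cytology or HSIL in the month-0 history. Report events in the remaining women separately.
- Note that HSIL is ascertained through routine care and is not attributed to an HPV type.

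The cost is wording plus a filter on the month-0 swab and the month-0 Pap and colposcopy history, both already collected. No visit or sample is added. The main rates will rest on fewer events and the claim is more modest. The filter is also imperfect: HSIL from non-vaccine types and infections acquired before the series is complete would still be counted, and the swab is tested with a research assay (section 12.2). These limits should be stated with the results.

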4.0 STUDY DESIGN

1. Design

The trial is a multicenter, observer-blind, randomized, phase IV clinical trial. All lab personnel assessing the primary endpoints are blinded to group allocation. For further details on observer blinding and randomization, please see section 5.2. Study sites are located in Vancouver, Regina, Winnipeg, Toronto, Hamilton, Montreal, and Quebec City.

2. Rationale

HPV vaccination has transformed the cervical cancer landscape, but current adolescent HPV vaccine programs alone will lead, at best, to elimination of cervical cancer in 80 years.²⁸ Reduction of disease burden and deaths requires more rapid elimination through: (i) scale up of screening and treatment and (ii) vaccine programs beyond adolescent-based models to prioritize additional age groups and key populations.²⁹

For persons who are immunocompromised, we do not have sufficient data on how to deploy HPV vaccines. WLWH are especially vulnerable; they are often marginalized and are least likely to engage in screening programs.³⁰ Importantly, HIV is a major global contributor to HPV incidence and cervical cancer development, resulting in significantly higher rates of disease among the world's 17.8 million WLWH.³¹ Therefore, global elimination strategies must include an evidence-based plan to immunize WLWH not only prior to sexual debut, but also across high-risk periods for HPV acquisition and into adulthood. Following the initial introduction of three-dose vaccine schedules, two-dose schedules have been adopted worldwide, based on robust studies conducted in immunocompetent girls and women,²³ and one-dose schedules are now being considered and recommended in some countries for the general population.¹⁷ However, it is still recommended that WLWH obtain 3 doses of vaccine due to a lack of data to support reduced dosing in this population.^{22, 32} This requirement of additional doses reduces the feasibility of vaccination for many women as well as the financial and logistic feasibility of vaccine programs in HIV-endemic countries.³³

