7.4.4.2 Indications for a Delay in Vaginal Swab Sampling

- Self-obtained samples may continue to be collected during pregnancy.

- Participants must not be menstruating at the time of the vaginal swabbing. The participant may have all other study procedures performed. The participant will be invited to take the swabs home to self-collect when they are not menstruating with instructions on how to return the swabs to the study centre.

7.4.4.3 **Indications for a Delay in Study Blood Sampling**

- Administration of immunoglobulins and/or any blood products within 30 days of study blood sampling
- Administration of any live virus vaccines given with 28 days of a blood sample
- Administration of inactivated or recombinant vaccines (e.g. Influenza, Hep B, Tdap, COVID) up to 8 days before study blood sample collection is acceptable

7.4.4.4 **Contraindication for Continuation of Study Procedures**

- Withdrawal from the study
- Anaphylactic reaction to HPV vaccine related component
- Development of any newly confirmed or suspected immunosuppressive or immunodeficient condition (other than HIV/AIDS)
- Administration of any HPV vaccine not provided as part of the study
- Investigator decides it is not in participant's best interest
- Participant decides to discontinue vaccine series

7.4.5 **Outline of Study Visits**

Month 0

At the Month 0 visit, the following will be done:

- Collection of informed consent.
- Baseline information will be recorded including information such as: general health history, HIV history and medication history, current antiretroviral medications
- A brief physical assessment (temperature, height, weight).
- Regular clinic and study bloodwork.
- A urine pregnancy test (regardless of age or sexual activity).
- A short questionnaire regarding how the participant feels about self-collecting a vaginal swab for the purpose of HPV screening for cervical cancer.
- A self-collected vaginal swab for detection of HPV DNA, and a retention swab.
- The first of three HPV vaccine doses will be given.
- Instructions regarding the 14-Day Post-Vaccine Symptom Diary

Month 1

At the month 1 visit the following will be done:

- Assess ongoing consent.
- Review of any changes in health status and/or medications.
- Review of all adverse events occurring in the first 14 days following vaccination and any significant adverse events following this period.
- Study bloodwork.

Month 2

This visit will only occur in participants in the routine group.

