7.5.2 Medical History

General Medical Systems History

A pre-existing health history including current medications will be collected at the first visit to ascertain a baseline prior to vaccination. The health history and medications/exposures will be updated at each subsequent visit. The baseline health assessment will be sufficiently detailed to confirm eligibility to participate and to identify a baseline for appropriate management of any SAEs that are reported.

Focused Medical History:

HIV diagnosis date & mode of acquisition if known; current HIV treatment, abnormal Pap tests, colposcopies, and treatments; history of genital warts and treatments; STIs; reproductive history will be ascertained at the Month 0 visit and updated at subsequent visits.

Please ensure at the comprehensive medical history is taken and documented prior to vaccination.

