12.0 LABORATORY METHODS AND ANALYSES

1. Antibody testing at Merck Laboratories

In order to attain comparability to licensure trial serologic results and comparable studies in immunocompetent persons, antibody assays will be conducted by our collaborator at Merck Laboratories, Q2 Solutions LLC, [name].

Each serum sample will be divided into 2 aliquots: #1 will go to the Merck laboratory for in-house serotesting and #2 will go to the BC Women's Research Lab (Women's Health Research Institute) for storage. Serum anti-HPV6, 11, 16, 18, 31, 33, 45, 52, and 58 immunoglobulin levels will be measured using competitive Luminex immunoassay (cLIA), and reported in arbitrary units (milli-Merck Units per ml [mMU/ml]) relative to the standard curves generated for each HPV type. Antibody titers are determined in a competitive format where type-specific labeled neutralizing antibodies for each type compete with patient serum antibodies for binding to conformation-sensitive neutralizing epitopes on virus like particles. Seropositivity is defined as > 50 mMU/ml for HPV6, 29 mMU/ml for HPV11, 41 mMU/ml for HPV16, 59 mMU/ml for HPV18, 29 mMU/ml for HPV31, 22 mMU/ml for HPV33, 15 mMU/ml for HPV45, 20 mMU/ml for HPV52, and 15 mMU/ml for HPV58.³⁶

2. HPV DNA Testing using Self-Collected Vaginal Swabs

All DNA testing for HPV will use vaginal swabs in STM vials. Swabs will be tested by [name] at the National Microbiology Laboratory, [name], using a commercially available research assay for the detection of high and low risk HPV genotypes.

We are utilizing a research HPV DNA assay not a clinical HPV assay, and we won't have the test results back in a timely manner as these will be run in batches, maybe 12-24 months after collection, possibly even more. The sensitivity and specificity of this test is not adequate for actionable results. The importance of participating in available clinical screening will be reinforced with participants during the course of study participation.

In cases where the same high risk HPV DNA type is found on 2 occasions, a minimum of 6 months apart, primary care providers will be notified and recommended to follow up with pap or HPV testing, or colposcopy.

3. Use of Retention Self-Collected Vaginal Swabs

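### HSIL incidence rates and Kaplan-Meier curves are planned, but no cytology is scheduled and negative screens are not listed for collection, so time at risk for HSIL cannot be established

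*Protocol*

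**What the plan says.** Section 3.0 (objective 7) sets out to study efficacy to month 24 "via persistent HPV infection with 9vHPV types, and cytological and histological HSIL". Section 13.5 item 4 gives the method: "we will calculate incidence rates of abnormal cervical cytology and histology (HSIL), and breakthrough persistent HPV infection", and "HSIL will be described with Kaplan-Meier curves". If numbers allow, curves are also to be drawn by age, CD4 count, HIV viral load and prior HPV status.

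The only cervico-vaginal sample in Tables 1A and 1B and in the visit outlines (7.4.5) is "A self-collected vaginal swab for detection of HPV DNA, and a retention swab". No visit includes a Pap test, cytology or colposcopy. The gynaecological history in 7.5.2, taken at Month 0 and updated later, covers "abnormal Pap tests, colposcopies, and treatments; history of genital warts and treatments", together with STIs and reproductive history.

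Screening is left to usual care. Section 12.2 says: "The importance of participating in available clinical screening will be reinforced with participants during the course of study participation". Of women living with HIV in general, section 4.0 says "they are often marginalized and are least likely to engage in screening programs".

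**The concern.** An incidence rate or a Kaplan-Meier curve needs events and also the time during which an event could have been seen. For HSIL that time is set by when each woman had a cervical test able to show it. The protocol arranges to collect the positive side (abnormal results, colposcopies, treatments) but not the negative side (normal results, their dates, or no test at all).

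This decides whether a stated objective can be interpreted. The HSIL rate would mix disease frequency with screening uptake in unknown proportion. The curves by CD4 count, viral load, age or prior HPV status could differ merely because some groups are tested more often. It is also more than a detail for the SAP: an SAP can define a censoring rule, but it cannot censor at a negative test that nobody was asked to record.

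**Working it through.** **Step 1. What each source in the protocol can supply.**

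| Source | Can add HSIL cases? | Must supply negative screens and dates? |
|---|---|---|
| Study visits (Tables 1A/1B, 7.4.5) | No; HPV DNA swab only | No |
| Focused history (7.5.2) | Yes; abnormal Paps, colposcopies, treatments | No |
| Routine clinical exams (7.4.1) | Possibly; documented where appropriate, cytology not named | No |
| Chart abstraction (7.5.4) | Not stated; covers HIV and general health status and blood tests | No |
| BC Cancer Registry linkage (7.5.11) | Yes; pre-cancer and cancer, consenting women, possibly years later | No |
| Chart review where there is no provincial registry (7.5.11) | Optional; cancer outcomes | No |

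Several sources add cases. None is required to supply the time at risk. A woman with a normal Pap at month 18 and a woman with no Pap at all would leave the same record in the items that 7.5.2 lists.

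**Step 2. Size.** The protocol states no HSIL rate, screening uptake or HSIL event count, so there is no planned figure to reproduce. The following is an illustration on assumed inputs.

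- Women followed: 450 × 0.90 = 405 (450 from section 5.0; 10% loss from section 10.3, which gives it to month 7 and is applied here to month 24 for simplicity).
- Follow-up: 2 years (section 7.4.1).
- Assumed: constant true rate r per person-year; share s of women whose HSIL would be detected; detection independent of disease; everyone else kept as event-free to month 24.
- True risk = 1 − exp(−2r). Observed risk = s × true risk. Relative understatement = 1 − s.

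| True rate per 100 person-years | True 24-month risk (events) | s = 0.4 | s = 0.6 | s = 0.8 |
|---|---|---|---|---|
| 1 | 1 − exp(−0.02) = 1.98% (8.0) | 0.79% (3.2) | 1.19% (4.8) | 1.58% (6.4) |
| 4 | 1 − exp(−0.08) = 7.69% (31.1) | 3.08% (12.5) | 4.61% (18.7) | 6.15% (24.9) |

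Over this range the understatement is 20–60%. It simply restates the assumed uptake, which is the point: uptake determines the answer and is not collected.

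**Step 3. Subgroup curves.** Suppose two subgroups share a true rate of 2 per 100 person-years, so a true risk of 1 − exp(−0.04) = 3.92%. With s = 0.4 in one and 0.8 in the other, the observed risks are 1.57% and 3.14%. A twofold gap appears with no difference in disease.

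**Step 4. Direction.** Downward is likely but not certain. With no baseline cytology scheduled, HSIL already present at enrolment and found later could be counted as incident. Section 12.2 also has primary care providers notified, with Pap, HPV testing or colposcopy recommended, when the same high-risk type is found twice at least 6 months apart. Testing is therefore directed partly at women at higher risk, although batch testing perhaps 12–24 months after collection may delay this.

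**The case against.** A reader might infer that the protocol counts unscreened women as disease-free. It does not say so. Section 13.5 gives no at-risk set, time origin or censoring rule for HSIL, Kaplan-Meier permits censoring at the last test, and such rules are commonly left to the SAP, which is not at hand. The missing censoring rule alone would be no finding. What stands is that the data such a rule would need are not listed for collection.

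A reader might also infer that only abnormal Pap tests are recorded. That is too narrow: 7.5.2 adds colposcopies and treatments, 7.4.1 allows routine exam results to be documented, and 7.5.11 adds linkage and optional chart review. The list in 7.5.2 is a summary, and the case report form, which is not shown, may ask for more. These sources improve case finding but, as written, do not oblige anyone to record a negative screen.

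Low uptake is not established for this cohort. The remark in section 4.0 concerns women living with HIV generally, whereas section 10.2 describes these participants as generally engaged in care. Nor is the loss irreparable, since past screening dates can be abstracted from charts retrospectively if the sites are asked to do it.

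Finally, restricting the analysis to tested women has its own bias. Being tested is a post-randomization event, partly prompted by persistent high-risk HPV (12.2), so estimates among tested women may be too high. That is a fair objection to a simple restriction, and the fix has to state it.

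**Conclusion.** The point holds as a defect in data collection. HSIL rates and curves are promised, no cytology or colposcopy is scheduled, and nothing requires negative results, test dates or absence of screening to be recorded. As specified, time at risk for HSIL cannot be established and coverage cannot be reported.

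The likely effect is understatement. If all women are kept at risk to month 24, its relative size is roughly the unscreened proportion. That rests on detection being independent of disease and on an uptake that the protocol does not give, so no figure can be attached to this trial.

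A reader might infer that the bias would make the vaccine look more protective. The documents do not support that as a stated consequence: there is no unvaccinated arm, all participants are scheduled for three doses, and section 13.5 item 4 plans no HSIL comparison between arms or with an external cohort. The outcome is exploratory and the subgroup curves are conditional on numbers. The primary and secondary analyses are untouched. The change is still worth making, because it is cheap and decides whether this part of the efficacy objective can be interpreted.

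**What to change.** **Section 7.5.2.** At Month 0 and at each update, record the date and result of every clinical Pap test, HPV test, colposcopy and histology, including normal results and an explicit 'none since last visit'. For women already enrolled, abstract the same items from charts retrospectively.

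**Section 13.5 item 4.**
- Count HSIL person-time only up to the last documented cytology or histology result.
- Flag HSIL known at baseline, and flag women without a baseline result, in whom prevalent disease cannot be excluded.
- Report the number screened by arm and by each subgroup for which a curve is drawn.
- State that testing is partly triggered by persistent high-risk HPV (12.2), so estimates among screened women may be selected upward.
- If coverage is too low, report detected HSIL cases with the number screened, in place of rates and curves.

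**Cost.** A few added fields and modest extra abstraction; 7.5.4 does not currently name cytology, so this is some new work for the sites. No participant procedure is added. The denominator shrinks, intervals widen, and some selection remains because tested women are not a random sample.
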